Complete Title: An evaluation of social media warning labels for teens and young adults: A randomized controlled trial

Short Title: Reactions to social media warning labels

Protocol Date: August 1, 2025

NCT #: 07199660

Study Principal Investigator:

[name]
Stanford University
email: [contact]

Protocol Synopsis

Study Title	Social Media Warning Labels
Funder	NA
Clinical Phase	NA
Study Rationale	
Among teens and young adults, average daily social media use is high and contributes to poor mental health and other adverse outcomes. Warning labels are a low-cost, highly scalable strategy for informing consumers about product harms and discouraging unhealthy behaviors.It remains unknown how teens and young adults respond to social media warnings, including which warning topics may be most effective at discouraging social media use and raising awareness of the harms of social media.
Study Objective(s)	The primary objective is to evaluate whether different social media warnings are perceived as effective at discouraging social media use and raising awareness of the harms of social media. A secondary objective is to compare perceived message effectiveness of warnings refined using artificial intelligence (AI) vs. those not refined using AI.
Study Design	Within-subjects randomized experiment.
Subject	Inclusion Criteria
Population	1. 13 to 29 years old
key criteria for key criteria for	2. Reside in the US
Inclusion and Exclusion:	3. Can read and speak English
Number of Subjects	1,000
Study Duration	Each subject's participation will last approximately 10 minutes. The enrollment period is expected to last ~4 weeks.
Study Phases	There are two phases: (1) Screening : screening for eligibility and obtaining consent and (2) Intervention : study intervention/experimental treatment.
Efficacy Evaluations	The primary outcome is perceived message effectiveness for discouraging social media use. It is measured with 1 survey item. The secondary outcome is perceived awareness of the harms of social media use. It is measured with 1 survey item.
Statistical and Analytic Plan	Primary outcome 
First, we will examine the effect of each social media warning topic on perceived message effectiveness compared to control.Second, we will examine the effect of each potential mandatory social media warning topic compared to a voluntary social media

warning. Third, we will test whether the effects of the social media warning topics in this study with human participants differ from the effects observed in a separate experiment conducted with artificial intelligence (AI) personas. Fourth, we will compare social media warnings we refined using AI personas to those we selected *a priori* and did not refine using AI.

Secondary outcomes

- We will examine the effect of each social media warning topic on awareness of the harms of social media compared to the control topic. We will also examine the effect of each potential mandatory social media warning topic compared to a voluntary social media warning.

Data and Safety Monitoring Plan

- The principal investigators are responsible for data quality management and ongoing assessment of safety.

Introduction

The primary goal of the analyses described here is to use data we collected through an online randomized experiment to examine consumer responses to different social media warning messages. These analyses examine the effect of warning topic (e.g., depression and anxiety, body image, sleep) on perceived message effectiveness (primary outcome) and perceived awareness of the harms of social media (secondary outcome).

A secondary goal of the analyses described here is to test whether the effects of the social media warning topics in this study with human participants differ from the effects observed in a separate experiment conducted with artificial intelligence (AI) personas. Another secondary goal is to examine whether warnings refined using AI are perceived as more effective than those selected *a priori* and not refined using AI.

This analysis plan pre-specifies the analyses before collecting data and therefore serves as our ex-ante planned analysis.

Study Protocol

Participants will complete a within-subjects online randomized experiment. After providing informed consent, participants will view and rate messages on perceived message effectiveness (primary outcome) and perceived awareness of the harms of social media (secondary outcome). Participants will view messages about 9 topics: 8 warning topics and 1 control topic. The 8 warning topics include 7 potential mandatory social media warnings (including the topics of depression and anxiety, body image, addiction, sleep, mental health harms to children, not been proven safe, and California's proposed warning) and 1 voluntary warning (similar to a message used on TikTok to encourage users to take breaks). For each topic, participants will view 1-2 messages and respond to survey items about that message. All messages will be shown in random order.

Statistical Considerations

General Principles

We will use a two-sided critical alpha of 0.05 as a criterion for all tests of statistical significance. All confidence intervals presented will be 95% and two-sided. We will follow intention-to-treat principles, including all participants who fully enroll in the study. We expect minimal missing data based on prior similar studies¹⁻³ but missing data will be accounted for under maximum likelihood assumptions in our mixed effects regression analysis of primary and secondary outcomes.

Primary Outcome

The primary outcome is perceived message effectiveness for discouraging social media use. We will measure perceived message effectiveness with 1 item adapted from prior studies,^{4,5} “How much does this message discourage you from wanting to use social media?” Response options will range from not at all (1) to a great deal (5).

Secondary Outcomes

The secondary outcome is reported increased awareness of the harms of social media. We will measure perceived awareness of the harms of social media with 1 item, “How much does this message increase your awareness of the harms of using social media?” Response options will range from not at all (1) to a great deal (5).

Statistical Methods

We plan to present results in two papers.

Paper 1 Analyses

1. Analyses of the primary outcome
 - a. We will use mixed effects linear regression to **evaluate the effect of each warning topic compared to the control topic on the primary outcome of perceived message effectiveness**. We will regress perceived message effectiveness on a set of indicator variables representing each social media warning topic (e.g., depression and anxiety, negative body image, sleep, etc.), excluding the control topic as the referent. We will treat the intercept as random to account for repeated measures within participants. The coefficients on the warning topics will give the average difference in mean perceived message effectiveness between each warning topic and the control topic. Given the exploratory nature of the study, we do not plan to correct *p*-values for multiple comparisons.
 - b. We will use the same mixed effects linear regression model to **evaluate the effect of each potential mandatory warning topic compared to the voluntary warning**.

- c. In exploratory analysis, we will test whether the effects of the warning topics on the primary outcome are possibly moderated by age (treated continuously), gender (male vs. female), and amount of social media use (treated continuously). To test for moderation, we will use mixed effects linear regression, regressing perceived message effectiveness on indicator variables representing each social media warning topic (excluding the control as the referent), the possible moderator, and the interactions between the possible moderator and the warning topics. We will center variables prior to analysis. We will use separate models for each moderator. We will test the joint significance of the interaction terms.
- d. We will also **descriptively rank the warning topics** on the primary outcome of perceived message effectiveness. We will estimate mean perceived message effectiveness for each social media warning topic (averaging across messages for each topic) and rank those means.

2. Analyses of the secondary outcome:

- a. We will use mixed effects linear regression to **evaluate the effect of each social media warning topic compared to the control topic on the secondary outcome of awareness of the harms or social media**. We will use the same approach as described for the primary outcome (see no. 1 above).
- b. We will use the same mixed effects linear regression model to **evaluate the effect of each potential mandatory warning topic compared to the voluntary warning**.
- c. We will **descriptively rank the social media warning topics** on the secondary outcome of perceived awareness of the harms of social media. We will estimate mean perceived awareness of the harms of social media for each topic (averaging across messages for each topic) and rank those means.

Paper 2 Analyses

1. Analyses of the primary outcome:

- a. We will test whether the effects of the social media warning topics in this study with human participants differ from the effects observed in a separate experiment conducted with artificial intelligence (AI) personas. We will compare the coefficient on each warning topic estimated in this study to the corresponding coefficient estimated in the separate experiment conducted with AI personas. We will pool data from this study with the data from the separate experiment conducted with AI personas and run a mixed effects linear regression, regressing perceived message effectiveness on indicator variables for each warning topic (excluding the control as the referent), an indicator variable for sample (i.e., whether the observation is from this study vs. the AI study), and the interaction between warning topic and sample. All variables will be centered. We will examine the coefficients on the interaction terms.

- b. We will compare how our human participants rate social media warnings we refined using AI personas to those we selected *a priori* and did not refine using AI. We will make this comparison both overall (pooling across all warning topics) and within each warning topic. These analyses will only include ratings from the 6 warning topics for which we tested both AI-developed and human-developed messages (depression and anxiety, negative body image, addiction, sleep, mental health harms to children, and not been proven safe).
 - i. First, we will use mixed effects regression, regressing perceived message effectiveness on an indicator variable for message source (AI-developed vs. human-developed) and treating the intercept as random. The coefficient on the indicator variable will indicate the average difference in means between AI-developed vs. human-developed messages.
 - ii. Second, we will run a set of mixed effects regressions, one for each warning topic. Each regression will regress perceived message effectiveness on an indicator variable for message source (AI-developed vs. human-developed), treating the intercept as random. The coefficient on the indicator variable will indicate the average difference in means between AI-developed vs. human-developed messages.

Sample Size Needs

We plan to collect data from 1,000 participants. We used G*Power⁶ to estimate sample size needs to detect an effect of each social media warning topic vs. control using ANOVA repeated measures (testing of within-subject factors). Assuming alpha=0.05, 2 measurements (given each contrast will compare 2 topics to one another), and a conservative correlation among repeated measures of 0.5 (based on prior studies⁷⁻⁹), a sample size of 900 would yield 85% power to detect effects of $f=0.05$ ($d=0.10$) or larger. This effect size would be considered small¹⁰ and is conservative based on our prior message development studies.^{8,9,11} We will recruit 1,000 participants to account for potential missing data.

Exclusions and Outliers

We will exclude human participants who do not complete the survey or who complete the survey implausibly quickly (defined as <1/3 of the median completion time). We will winsorize outlier values defined as more than 3 interquartile ranges below or above the 25th and 75th percentiles of the observed distributions (i.e., Tukey far outliers). These participants and winsorized observations will be included in the analysis.

References

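### Display position is randomised but enters none of the human-data models, so any average drift in the ratings would cost some precision; a prespecified position term is a free improvement

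*SAP*

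**What the plan says.** Under Study Protocol, the SAP describes a within-subjects experiment: "Participants will view messages about 9 topics: 8 warning topics and 1 control topic". It adds that "For each topic, participants will view 1-2 messages and respond to survey items about that message", and that "All messages will be shown in random order".

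The SAP lists its regressors. In Paper 1, 1a, the fixed part is given by "We will regress perceived message effectiveness on a set of indicator variables representing each social media warning topic", and the only random term is a participant intercept: "We will treat the intercept as random to account for repeated measures within participants". Item 1b reuses that model for the comparison with the voluntary warning, 1c adds one moderator and its interactions, and 2a-2b carry the approach over to the secondary outcome. In Paper 2, 1b(i), the model is described as "regressing perceived message effectiveness on an indicator variable for message source (AI-developed vs. human-developed) and treating the intercept as random"; 1b(ii) fits the same model topic by topic.

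Display position, or order, appears in none of these models, and no sensitivity analysis for order is stated.

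**The concern.** Every participant answers the same two items about one message after another in a single sitting. Ratings may move along such a sequence through fatigue, habituation, or a first rating given before the person has anything to compare it with. Position is randomised and known for every rating, much like period in a crossover.

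A random intercept absorbs only what is constant within a person. Average drift differs from one rating to the next within the same person, so it enters the residual. Random order keeps it from biasing the topic and source contrasts but does not remove its variance. A robust variance estimator would not recover the loss either.

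What is at stake is precision only: the width of the intervals for topic versus control, mandatory versus voluntary and AI-developed versus human-developed messages. This is separate from carry-over between two messages on the same topic.

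**Working it through.** **Inputs from the SAP (Sample Size Needs).** N = 900, f = 0.05 (d = 0.10), correlation 0.5, 2 measurements, alpha 0.05, power 85%.

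**Number of ratings.** Paper 2, 1b refers to "the 6 warning topics for which we tested both AI-developed and human-developed messages". If the other three topics have one message each, a participant gives 6 × 2 + 3 × 1 = 15 ratings. The SAP does not state this figure; one to two messages on each of 9 topics allows 9 to 18.

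**Assumptions that are not in the SAP.** Rating SD 1.2, and linear drift of 0.25 to 1.0 points from first to last message.

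**Step 1: the plan's own figure.** Non-centrality = f² × N × m / (1 − ρ) = 0.0025 × 900 × 2 / 0.5 = 9.0. With 1 and 899 degrees of freedom, power is 0.850. The stated 85% reproduces.

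**Step 2: variance added by drift.** Under random order, linear drift of D (in SD units) over J positions adds v = D² × [J(J + 1)/12] / (J − 1)² to the within-person residual, in units of SD². For J = 15 this is D² × 20/196 = 0.102 D². The residual without drift is 1 − ρ = 0.5, so the variance ratio is R = 1 + v/0.5. A position term reduces the standard error by 1 − 1/√R.

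| Drift (points) | D = drift/1.2 | v | R | SE reduction |
|---|---|---|---|---|
| 0.25 | 0.208 | 0.0044 | 1.009 | 0.4% |
| 0.5 | 0.417 | 0.0177 | 1.035 | 1.7% |
| 0.75 | 0.625 | 0.0399 | 1.080 | 3.8% |
| 1.0 | 0.833 | 0.0709 | 1.142 | 6.4% |

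A simulation of the topic model (900 participants × 15 ratings, with and without 14 position indicators) gave SE ratios of 0.996, 0.984, 0.963 and 0.936, that is, reductions of 0.4%, 1.6%, 3.7% and 6.4%. With no drift the ratio was 1.0006, a cost of about 0.06%. A second simulation, with a linear position term, found the same proportional widening for the topic-control, topic-voluntary and AI-versus-human contrasts: about 2.5% for all three at a drift of 0.5 SD.

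**Step 3: power at d = 0.10 and N = 900 without the term, if the plan's correlation is free of drift.** The plan's calculation compares two single measurements, with contrast variance proportional to 1 + 1 = 2. A two-message topic against a single-message one has 1/2 + 1 = 1.5, so its non-centrality is 9 × 2/1.5 = 12. Dividing each by R gives:

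| Drift (points) | Single-message pair (9/R) | Two-message vs single-message topic (12/R) |
|---|---|---|
| 0 | 85.0% | 93.3% |
| 0.5 | 83.8% | 92.5% |
| 0.75 | 82.2% | 91.5% |
| 1.0 | 80.1% | 90.0% |

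On the 15-rating reading, the first column covers only pairs among the California, voluntary and control messages. The second covers six of the eight warning-versus-control contrasts and six of the seven mandatory-versus-voluntary ones.

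**Step 4: if the correlation of 0.5 already contains drift.** The residual free of drift is then 0.5 − v. At a drift of 0.5 points the non-centrality with a position term is 9 / (1 − 0.0177/0.5) = 9.33, and power is about 86%. The term then raises power above 85%.

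**The case against.** The strongest reply is that the SAP already handles order through randomisation, that nothing in it is wrong, and that adding a prognostic covariate for a small gain is a matter of taste. Much of this stands. The contrasts are unbiased and the intervals valid without the term. The SAP offers no evidence of drift, and participation lasts only about 10 minutes. A full-point average drift on a 1-5 scale would be large, and below about 0.3 SD the loss in standard error is under 1%. The 15 ratings are inferred. A fixed term also removes only average drift, not drift that differs between people.

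A reader might infer three stronger things, none of which the SAP supports:

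- **That the study is underpowered.** The fall towards 80% needs a one-point drift and applies only to single-message pairs. It also requires a correlation free of drift, yet the SAP takes its 0.5 from prior studies; if their ratings contained drift, the 85% already allows for it.
- **That intervals are in fact being widened.** This depends on drift being present, and no drift figure is given.
- **That the descriptive ranks in 1d and 2c are distorted.** The chance difference in mean position between two single-message topics has SD √(15 × 16 / 6 / 900) = 0.21 positions. With 14 steps from first to last, that is 0.21 × 0.5/14 = 0.008 points for a 0.5-point drift and 0.015 for a 1.0-point drift, which is negligible.

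The reply does not remove the imbalance between cost and benefit. The SAP presents itself as the analysis fixed before data collection, so a position term not named now would be a post hoc choice.

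**Conclusion.** The point holds as a conditional, minor matter of precision. No human-data model contains the randomised display position, so any average drift would stay in the residual. The likely stake is a few per cent of standard error at most. In sample-size terms (R − 1), drifts of 0.5 to 1.0 points correspond to about 3% to 14% more participants. These figures rest on the assumed SD of 1.2, 15 ratings, linear drift and the plan's correlation of 0.5; the power losses also require that this correlation be free of drift. This is a free improvement, not an error in the plan.

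**What to change.** In Paper 1 (1a-1c, 2a-2b) and Paper 2, 1b(i)-(ii), prespecify display position as a fixed effect: categorical in general (14 indicators if there are 15 positions), and a linear term in the per-topic models of 1b(ii). Leave the topic and source contrasts unchanged. Keep the display order of every message with its rating in the analysis data set.

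The cost is one sentence in the SAP, one stored variable, and 14 of more than 12,000 within-person degrees of freedom (900 × 14 = 12,600 before the topic terms). Sample size and survey length do not change.

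### The analysis is labelled intention-to-treat, but the exclusion rule removes non-completers and fast completers

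*SAP*

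**What the plan says.** The SAP describes the analysis set in two places.

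- **General Principles** (under Statistical Considerations): "We will follow intention-to-treat principles, including all participants who fully enroll in the study". On missing data it adds that "missing data will be accounted for under maximum likelihood assumptions in our mixed effects regression analysis of primary and secondary outcomes". It expects little missing data.
- **Exclusions and Outliers**: "We will exclude human participants who do not complete the survey or who complete the survey implausibly quickly", the speed cut-off being one third of the median completion time. After a sentence on winsorizing, the section ends: "These participants and winsorized observations will be included in the analysis".

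Three other statements bear on what enrolment means and on whether partial data are usable.

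- The Protocol Synopsis describes the Screening phase as "screening for eligibility and obtaining consent" and places it ahead of the Intervention phase.
- Study Protocol says "After providing informed consent, participants will view and rate messages on perceived message effectiveness".
- The same section says "All messages will be shown in random order".

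The SAP does not define *fully enroll*.

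**The concern.** Both exclusions depend on what participants do after consent, and speed can be judged only once the survey is finished. The set that remains is a speed-filtered set of completers, which is not what an intention-to-treat label tells a reader.

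Removing every non-completer also leaves maximum likelihood little to do: it would cover only items that completers skipped. The random-intercept model in Paper 1 Analyses accepts unequal numbers of ratings per person. Ratings given before someone stops could therefore be used under missing-at-random.

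Two things are at stake. The papers could carry a label that does not describe their analysis set, and usable ratings would be thrown away. The same human data feed both outcomes and both planned papers.

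**Working it through.** **1. The passages side by side**

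| Participant | General Principles | Exclusions and Outliers |
|---|---|---|
| Consents, stops part-way | In, if enrolment means consent; out only if it means completion, which is not stated | Out |
| Consents, finishes in under 1/3 of the median time | In on either meaning | Out |
| Finishes at normal speed, skips items | In, by maximum likelihood | In |

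The second row conflicts on any reading. The first conflicts unless *fully enroll* means completed.

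The closing sentence of Exclusions and Outliers does not settle it. The only participants named before it in that section are the excluded ones, so read literally it reverses the exclusion. If it means participants with winsorized values, which is more likely, the conflict with General Principles remains.

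**2. The plan's own figure**

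Sample Size Needs gives N = 900, f = 0.05, m = 2 measurements, correlation ρ = 0.5 and alpha 0.05. For a within-subject factor, the noncentrality is

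λ = N·m·f²/(1 − ρ) = 900 × 2 × 0.0025 / 0.5 = 9.0.

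With a noncentral F on 1 and 899 degrees of freedom, power is 0.850. The stated 85% reproduces. The 1,000 to be recruited allow for 10% loss: 900/(1 − 0.10) = 1,000.

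**3. Ratings discarded**

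Assumed layout: Paper 2 Analyses lists 6 topics with both an AI-developed and a human-developed message. Taking 2 messages for each of these and 1 for each of the other 3 topics gives 6 × 2 + 3 × 1 = 15 ratings per person per outcome, or 15,000 for 1,000 people. The SAP gives no stopping rate, so the share q who stop is also assumed. With the stop point uniform on 1 to 14, a person who stops has given (1 + 14)/2 = 7.5 ratings on average. Ratings discarded = 1,000 × q × 7.5.

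**4. Precision lost**

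For a person with topic design matrix X and covariance V = (1 − ρ)I + ρJ (J is the all-ones matrix), the information on the 9 topic means is XᵀV⁻¹X. Let A be its value for a completer and B its average over people who stop part-way, with messages in random order, missing-at-random and 20,000 draws. For a contrast c of a topic against control,

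variance ratio = cᵀ[(1 − q)A + qB]⁻¹c ÷ cᵀ[(1 − q)A]⁻¹c,

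and the cut in standard error is 1 − √ratio. With an intraclass correlation of 0.5 (the plan's ρ):

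| Assumed q | Ratings discarded | Ratio, two-message topic | Ratio, one-message topic | Cut in SE |
|---|---|---|---|---|
| 2% | 150 | 0.9905 | 0.9905 | 0.5% |
| 5% | 375 | 0.9759 | 0.9758 | 1.2% |
| 10% | 750 | 0.9505 | 0.9503 | 2.5% |
| 20% | 1,500 | 0.8952 | 0.8948 | 5.4% |

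Example at 10%: 1 − √0.9505 = 1 − 0.975 = 2.5%.

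Varying the intraclass correlation over 0.3, 0.5 and 0.7, with one or two control messages, gives 2.48–2.58% at q = 10% and 5.33–5.54% at q = 20%.

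**The case against.** The strongest reply is that the analysis set is in practice settled. Exclusions and Outliers gives an explicit numeric rule fixed in advance, and an analyst would apply it over a general statement of principle. The label also does less work in a within-subjects design, where there are no arms to unbalance. *Fully enroll* could be read as completed, and maximum likelihood for items skipped by completers is coherent. The plan has a margin too: if the 1,000 are counted before exclusions, power is 85.0% with 10% excluded and 80.7% with 20%.

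Much of this stands, and it limits the size of the problem. It does not remove it. If the specific rule governs, the intention-to-treat label is wrong for fast completers whatever *fully enroll* means, and for non-completers unless an unstated meaning is supplied. The closing sentence needs rewording in any case.

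Three further points are fair:

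- The layout and stopping pattern are assumed. With little missing data expected, the low end of the table is the relevant part.
- People who rate every message but leave later survey items blank are also non-completers, and the calculation does not model them.
- Participants who stop part-way have no completion time, so the speed rule cannot screen them if their ratings are kept. This residual affects few ratings and does not undo the remedy.

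**Conclusion.** The concern holds and should be fixed. The stated analysis population and the exclusion rule contradict each other. The conflict over fast completers is unconditional; the one over non-completers depends on the ordinary reading that enrolment precedes rating.

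The practical effect is modest. Under the assumed layout, a random stopping point and missing-at-random, keeping partial ratings improves the standard error by about 0.5% at 2% stopping and 5.4% at 20%. No loss of the planned power and no bias is claimed, and the sample size calculation is not in error. The main cost of leaving the text as it is would be a published label that misdescribes the analysis set.

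**What to change.** Define one primary analysis set and use it in both General Principles and Exclusions and Outliers:

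- Include eligible, consenting participants with at least one rating, less completers who finish in under 1/3 of the median completion time.
- Keep the available ratings of participants who stop part-way in the maximum-likelihood mixed model, for both outcomes.
- Describe the speed rule as a pre-specified data-quality exclusion, and state that it cannot be applied to people without a completion time.
- Drop the intention-to-treat label and the term *fully enroll*.
- Report one sensitivity analysis of all participants with at least one rating.
- Reword the last sentence of Exclusions and Outliers to say only that participants with winsorized values remain in the analysis.

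The cost is a few sentences, one further model run and the loss of the label. Design and sample size do not change. Using partial ratings relies on missing-at-random. If stopping depends on unrecorded reactions to the messages, keeping those ratings does not remove that problem.

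### The seven mandatory warning topics are compared with one another only by ranking observed means, with no test or interval for the differences between them

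*SAP*

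**What the plan says.** The Study Rationale in the Protocol Synopsis gives as part of the knowledge gap "which warning topics may be most effective at discouraging social media use and raising awareness of the harms of social media". The formal objective is narrower: "The primary objective is to evaluate whether different social media warnings are perceived as effective at discouraging social media use", and likewise for raising awareness.

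On design, the Study Protocol section says "Participants will view messages about 9 topics: 8 warning topics and 1 control topic", and "The 8 warning topics include 7 potential mandatory social media warnings"; the eighth is the voluntary message.

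The topic comparisons under Paper 1 Analyses are:

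- 1.a, and 2.a for the secondary outcome: each warning topic against control, from a random-intercept model with an indicator for every warning topic.
- 1.b and 2.b: each mandatory topic against the voluntary message, from the same model.
- 1.c: moderation by age, gender and amount of social media use.
- 1.d: "We will estimate mean perceived message effectiveness for each social media warning topic (averaging across messages for each topic) and rank those means".
- 2.c: the same for awareness, that is, "perceived awareness of the harms of social media for each topic (averaging across messages for each topic) and rank those means".

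The Paper 2 analyses compare human with AI-persona samples and AI-refined with unrefined messages. None of the tested contrasts sets one mandatory topic against another. Items 1.d and 2.c are labelled descriptive and mention no interval, either for a rank or for a difference between topics.

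**The concern.** A ranking of seven estimates always has a first place, whether or not the underlying means differ. The intervals the plan will produce are for differences from control or from the voluntary message. They do not give the uncertainty of a difference between two mandatory topics, and that one topic has a larger coefficient than another does not show that it is better.

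At stake is what Paper 1 can say about the part of its rationale that asks which topics work best. As written, a reader would see the size of the gaps between means but would have no planned way to judge whether a lead exceeds chance. Without a pre-specified comparison there is also room for selective pairwise testing once the order is known.

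**Working it through.** **Inputs.** From Sample Size Needs: 900 analysed, correlation 0.5, two measurements per contrast, f = 0.05 (d = 0.10), 85% power. From General Principles: two-sided alpha 0.05. From the Study Protocol section: seven mandatory topics, hence 7 × 6 / 2 = 21 pairs, with one or two messages per topic. Assumptions: total SD 1; six mandatory topics with two messages each (the six listed in Paper 2, item 1.b) and the California warning with one; equal correlations unless stated otherwise.

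**1. The plan's own figure.** Noncentrality = n × m × f² / (1 − ρ) = 900 × 2 × 0.0025 / 0.5 = 9.0. The noncentral F with 1 and 899 df gives power 0.850, so the stated 85% reproduces. The formula does not depend on which two topics are compared, so it applies equally to any single pair of mandatory topics.

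**2. Spread of observed means when all seven topics are equal.** The within-person error variance of a topic mean is 0.5 / (k × 900), with k messages. By simulation, the expected gap between the top and bottom observed means is:

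- one rating per topic: 0.064 SD;
- six topics with two messages, one with one: 0.048 SD.

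**3. How often the truly best topic ranks first** (one rating per topic, one topic leading six equal ones): 36% for a lead of 0.02 SD, 51% for 0.03, 76% for 0.05 and 99% for 0.10.

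**4. Standard error of a difference between two topics, n = 900.**

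- One rating each: √(2 × 0.5 / 900) = 0.0333; 95% half-width 1.96 × 0.0333 = 0.065 SD.
- Two messages each: √(2 × 0.25 / 900) = 0.0236; half-width 0.046 SD.
- Two messages against one: √((0.25 + 0.5) / 900) = 0.0289.
- Two messages each, with 0.2 of the within-person variance of 0.5 due to personal topic preference: the per-topic variance is 0.2 + 0.3 / 2 = 0.35, so √(2 × 0.35 / 900) = 0.0279; half-width 0.055 SD.

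The last line matters for the choice of standard error. Averaging two messages does not reduce the preference component, and a random intercept alone does not model it. In this example the model would work with about 0.0236 where 0.0279 is right.

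**5. Power for one pair at a true difference of 0.10 SD.** The Tukey critical value for seven means is 2.95; power is Φ(0.10 / SE − critical value).

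| Basis | Unadjusted (1.96) | Tukey (2.95) |
|---|---|---|
| One rating each | 85% | 52% |
| Two messages against one | 93% | 70% |
| Two messages each, preference variance 0.2 | 95% | 74% |
| Two messages each, no preference variance | 99% | 90% |

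With 21 unadjusted pairs, the chance of at least one false difference among seven equal topics is about 44% by simulation, which is why the adjusted column is the relevant one.

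**6. Joint 6-df test, one rating per topic.** Noncentrality = 900 × Σ(mean − grand mean)² / 0.5. With one topic 0.10 SD above six equal ones: 900 × 0.00857 / 0.5 = 15.4, power 85%. With seven means evenly spaced over 0.10 SD: 900 × 0.00778 / 0.5 = 14.0, power 81%.

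**The case against.** The plan does not promise more than it delivers. The question of which topics are most effective appears only in the rationale; the formal objective asks whether the warnings are perceived as effective, and each analysis listed in the synopsis has a matching model. The ranking is called descriptive, the study is described as exploratory, and nowhere is the top topic to be declared superior. All of this stands. A reader might infer that the plan fails its primary objective or contradicts itself; the document supports neither reading.

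A reader might also infer that the data would settle the order easily, since an unadjusted comparison of two two-message topics has 99% power at 0.10 SD. That is the most favourable pair without adjustment. Adjusted over 21 pairs the figure is 52% to 90%, and for a lead of 0.03 SD it is 5% or less. The added analysis would often show only that topics cannot be separated.

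It is also true that readers will see the estimated means and not bare ranks, and that misordering is likely mainly for leads well below the 0.10 SD that the plan itself calls small. Finally, intervals from the random-intercept model would be too narrow if people differ in topic preference, and with one or two messages per topic a topic comparison depends partly on particular wordings. The first of these can be handled by the choice of standard error; the second is a limit to state.

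What remains is that neither the descriptive label nor the exploratory purpose is a reason to leave a planned comparison, on both outcomes, without any measure of its uncertainty.

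**Conclusion.** The point holds as a gap between rationale and analysis and as a cheap improvement; it is not an error in the plan's figures. Items 1.d and 2.c are the only places where mandatory topics are compared with each other, and they give no test or interval for the differences. Under equality the observed means would still spread over about 0.05 to 0.064 SD, and a topic truly ahead of six equal ones by 0.02 to 0.05 SD would rank first between 36% and 76% of the time on a one-rating basis.

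These figures assume 900 analysed, a correlation of 0.5 and equal correlations. The SAP fixes no other correlation. Over an assumed range, unadjusted power for one pair at 0.10 SD (one rating each, n = 900) is 72% at 0.3 and 97% at 0.7.

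**What to change.** In items 1.d and 2.c, keep the ranking and add:

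1. A 6-df joint test that the seven mandatory topics have equal means.
2. The 21 pairwise differences among them with Tukey- or Holm-adjusted 95% confidence intervals, or, in their place, bootstrap 95% intervals for the ranks, resampling participants.
3. Participant-clustered robust standard errors, or within-person paired differences, so that variation in topic preference does not make the intervals too narrow.
4. A sentence that no topic will be called more effective than another on rank alone.

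The model in 1.a already holds every topic indicator, and 1.b already uses it for contrasts other than with control. The cost is therefore some post-estimation code and one table, with no new data. The downside is more contrasts to report, and the paper may have to say that the top topics cannot be separated.
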